Proximal SSL per colonoscopy, mean (SD)	0.03 (0.22)	0.10 (0.58)	[†] 0.036

*Fisher exact test. [†]Student's *t* test

Hypotheses

We hypothesize that the combination of WE and AI will significantly increase APC as opposed to WE alone, in patients undergoing screening or surveillance colonoscopy. The primary outcome of this study is APC. We aim to confirm whether the combination of WE with AI achieves a significantly higher APC than WE alone.

Methods

Study design: The WEAID (WE-AI-assisted Detection) trial is a two-arm parallel multicenter RCT designed to compare APC between WE with AI and WE colonoscopy

alone. Patient recruitment will be conducted at three hospitals in Italy and Taiwan (Digestive Endoscopy Unit, CTO Hospital, Iglesias, Italy [primary investigator: [name]]; Digestive Endoscopy and Gastroenterology Unit, Manzoni Hospital, Lecco, Italy [primary investigator: [name]]; and Evergreen General Hospital, Taoyuan, Taiwan [primary investigator: [name]]). Ethical approval will be sought from the Institutional Review Boards of the participating centers. Informed written consent will be obtained from all enrolled patients. The trial has been registered with ClinicalTrials.gov and assigned the identifier NCT06173258 before patient enrollment. The Sepulveda Ambulatory Care Center, VAGLAHS, UCLA in the USA will be a non-recruiting participating site.

Study population: The study population include male and female patients aged 45–75 years at average risk for CRC who plan to undergo colonoscopy for primary screening, postpolypectomy surveillance, and individuals with positive fecal immunochemical test (FIT) or guaiac fecal occult blood test (gFOBT) results. The exclusion criteria incorporate (1) patients with a history of inflammatory bowel disease, hereditary CRC syndrome, serrated polyposis syndrome, CRC, colorectal resection, colonic stricture, or severe comorbid illnesses rendering polypectomy unsafe; (2) patients with colonoscopy contraindications (e.g., acute diverticulitis or toxic megacolon); (3) therapeutic colonoscopy (e.g., hemostasis, removal of a large polyp); (4) emergent colonoscopy; (5) pregnant women or those planning pregnancy; and (6) patients unwilling to participate in the study.

Study investigators: All study investigators will be experts with a minimum of 500 completed WE colonoscopies. Additionally, each investigator will exhibit a minimum baseline ADR of 25%.

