Sample size calculation: For group comparison, the sample size was determined assuming that the APC of the control group is 0.9. A clinically significant relative increase of 25% in APC was considered. With a two-sided significance level of 5% and 80% power, 376 patients will be required per group (752 randomized patients). Accounting for a 10% overall dropout rate, enrollment of at least 836 patients is planned.

Statistical analysis: Categorical variables are presented as frequencies and percentages and continuous variables as means with standard deviations. The analysis will follow the intention-to-treat approach. Student's *t*-test will be used for continuous variables and chi-square test will be used for categorical variables. Poisson regression will be used to calculate incident rate ratios comparing the APC between the two arms, adjusting for age, sex, body mass index, smoking history, CADe system, and bowel preparation quality. A planned interim analysis will be conducted after the recruitment of approximately 70% of the planned enrollment to determine whether early termination of the study is appropriate to minimize the number of patients in the control group given the less effective, or clearly inferior

treatment. All statistical analyses will be performed using Python version 3.10 (SciPy Library). A *P* value < 0.05 is considered significant.

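### The interim look at about 70% of enrolment can stop the trial for efficacy, but no stopping boundary or adjusted final alpha is set; P < 0.05 at both looks would give about 6.3% to 7.6% type I error, not 5%

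*Combined protocol and SAP*

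**What the plan says.** The Statistical analysis section plans one interim look: "A planned interim analysis will be conducted after the recruitment of approximately 70% of the planned enrollment". Its purpose is "to determine whether early termination of the study is appropriate", and the reason given for stopping is "to minimize the number of patients in the control group given the less effective, or clearly inferior" treatment. The same section says that a P "value < 0.05 is considered significant", without limiting this to the final analysis.

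Two analyses could apply to adenomas per colonoscopy (APC). Student's t-test is assigned to continuous variables in general, and "Poisson regression will be used to calculate incident rate ratios comparing the APC between the two arms". Neither is named as the interim test.

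The Sample size calculation is made "With a two-sided significance level of 5% and 80% power". It arrives at 376 per group (752 in total), and after a 10% dropout allowance "enrollment of at least 836 patients is planned". It does not mention the interim. No section gives an interim threshold, a boundary, a spending function or an adjusted final level, and none refers to a separate document that would hold them.

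**The concern.** Deciding whether control is the worse arm requires an unblinded comparison of efficacy, so the interim is a second opportunity to declare a difference. If each of two looks is tested at the full level, the chance of at least one false positive exceeds that level. The Hypotheses section states a confirmatory purpose: "We aim to confirm whether the combination of WE with AI achieves a significantly higher APC than WE alone". The error rate attached to a positive result is therefore central to what the trial can claim. With no rule fixed in advance, a reader cannot tell what error rate applies to a positive finding at either look, and a rule chosen after interim data have been seen could not credibly repair this.

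**Working it through.** **The plan's own figures.** The dropout step reproduces: 752 / 0.90 = 835.6, rounded up to 836. The 376 per group cannot be derived from the stated inputs alone, because no standard deviation (SD) is given. With a difference of 0.25 × 0.9 = 0.225 and an assumed SD of 1.10, the usual formula gives

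n = 2 × (1.960 + 0.842)² × 1.10² / 0.225² = 375.2, rounded up to 376.

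This match uses a single test at two-sided 5% with no inflation for an interim. The error rates below do not depend on the SD, the APC or the sample size. They depend only on the information fraction and the critical values.

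**Inputs.**
- Critical value 1.960 at both looks. This is the P < 0.05 of the Statistical analysis section, applied twice by assumption because no other threshold is given.
- Information fraction t = 0.70, from the stated interim timing.
- Range for t: 70% of 836 is 585 enrolled. If all 585 are evaluable and the final analysis has 752, t = 585/752 = 0.78. The lower end, 0.65, is an assumption that allows for the word ‘approximately’.

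**Method.** With no true difference, the interim and final statistics (Z1, Z2) are bivariate normal with correlation √t, which is √0.70 = 0.837. Positive values favour AI.
- False claim for AI: P(Z1 > 1.96 or Z2 > 1.96).
- Overall error, interim stop only for AI, two-sided final test: P(Z1 > 1.96 or |Z2| > 1.96).
- Overall error, interim stop in either direction: P(|Z1| > 1.96 or |Z2| > 1.96).

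| t | False claim for AI | Overall, stop only for AI | Overall, stop either way |
|---|---|---|---|
| 0.65 | 3.88% | 6.38% | 7.77% |
| 0.70 | 3.78% | 6.28% | 7.56% |
| 0.75 | 3.67% | 6.17% | 7.34% |
| 0.78 | 3.60% | 6.10% | 7.19% |

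At t = 0.70 the columns agree with each other: 3.78% + 2.50% = 6.28%, and 2 × 3.78% = 7.56%. A simulation of 4 million trials at t = 0.70 gave 3.79%, 6.29% and 7.57%.

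**Boundaries that hold 5%, at t = 0.70.**
- *O'Brien-Fleming-type (Lan-DeMets) spending, 0.025 per side.* Alpha spent per side at the interim is 2 × [1 − Φ(z₀.₉₈₇₅/√t)], which gives an interim critical value of 2.438 (two-sided P < 0.0148). Solving for the final value so that the total is 5% gives 2.000 (P < 0.0455). The false-claim rate for AI is then 2.50%.
- *Haybittle-Peto, interim P < 0.001.* The exact final level is 0.04996. Leaving the final test at 0.05 gives 5.004% overall.

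**Power**, with expected final statistic 1.960 + 0.842 = 2.802: 79.4% under O'Brien-Fleming-type spending and 80.0% under Haybittle-Peto. Restoring 80% under the former needs a factor of 1.015: 752 × 1.015 = 763.3, about 764 evaluable, and 764 / 0.90 = 848.9, about 849 enrolled.

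**The case against.** The strongest reply is that the inflation is hypothetical. The document defines what counts as significant; it does not say that this definition governs early termination. A reference to a clearly inferior treatment could fit a strict criterion, and with interim P < 0.001 and an unadjusted final test the overall error is 5.004%. This stands as a limit on the figures: they are conditional. It does not remove the defect. The same phrase also admits a treatment that is merely less effective, neither expression has a numerical meaning, and a rule that is not written cannot be credited.

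Four narrower points also deserve weight.
- The text describes stopping to spare control patients, not stopping in favour of control. The figures closest to the wording are therefore 6.3% overall and 3.8% in favour of AI; 7.6% applies only if a stop in either direction is allowed.
- APC is the sole primary outcome, so it is the natural reading of the interim outcome. The choice between t-test and Poisson regression remains open, but that affects the final analysis too.
- A sample size without an interim allowance is not in itself an error, because the cost of a proper boundary is between nothing and 0.6 points of power.
- All the error rates assume a correctly calibrated test. The pilot variance-to-mean ratios in Table 1 are 1.38²/1.14 = 1.67 and 1.80²/1.31 = 2.47. If such overdispersion persisted after covariate adjustment, Poisson regression with model-based standard errors would exceed 5% even at one look. That is a separate issue and does not help the plan here.

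**Conclusion.** The concern holds, and it must be fixed before the interim. The established defect is an efficacy look with power to stop and no prespecified decision rule. Its size depends on the rule actually used. Under the only threshold in the document, applied at both looks, overall type I error is about 6.3% (6.1% to 6.4% over t = 0.65 to 0.78) if only a result favouring AI can stop the trial, and about 7.6% (7.2% to 7.8%) if either direction can. The excess over 5% is thus 1.1 to 2.8 percentage points. The false-claim rate for AI is about 3.8% (3.6% to 3.9%) against 2.5%, roughly one and a half times the intended rate. Under a very strict unwritten interim rule the excess would be negligible. These results assume a single interim look, the stated range for the information fraction, and a valid test at each look.

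**What to change.** Before any interim data are seen, amend the Statistical analysis section to:

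1. name APC as the interim outcome and state the one test that governs it at both looks;
2. state whether the interim can stop the trial in one direction or both;
3. replace the general P < 0.05 for the primary outcome with a boundary that preserves the overall 5%.

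Either of these would serve, and the choice is the sponsor's:

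- **O'Brien-Fleming-type spending:** interim two-sided P < 0.0148 and final P < 0.0455 at t = 0.70, recomputed at the actual fraction (0.0109 then 0.0466 at 0.65; 0.0223 then 0.0434 at 0.78).
- **Haybittle-Peto:** interim P < 0.001 and final P of about 0.05.

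The text change is two or three sentences. The first option lowers power from 80.0% to 79.4% at the planned size, or needs about 12 more evaluable patients (752 to 764) and 13 more enrolled (836 to 849) to restore 80%. The second keeps power at 80.0% and adds no patients.

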Official Title: Evaluation of Artificial Intelligence for Adenoma Detection in Water Exchange Colonoscopy: the WEAID Randomized Controlled Trial (Water Exchange With Artificial Intelligence-assisted Detection)

NCT number: 06173258

Date of Document: Oct 1, 2023.

Introduction

Adenoma detection rate (ADR) and adenoma per colonoscopy (APC) are crucial predictors for postcolonoscopy colorectal cancer (CRC). Water Exchange (WE) colonoscopy maximizes bowel cleanliness during insertion and has demonstrated superiority in increasing ADR and APC as compared to air insufflation.

Artificial intelligence (AI) lesion computer-aided detection (CADe) devices present promising tools for colonoscopies. Meta-Analysis reveals that AI generates an average ADR gain of 8% and an average APC gain of 0.20 in air-insufflated colonoscopy.

Recent research confirmed that the addition of AI to WE elevated ADR, and the application of WE to AI reduced false positive (FP) instances per colonoscopy, as evidenced by the analysis of pre-recorded video in a randomized controlled trial (RCT) comparing WE and air insufflation. Pilot retrospective data involving 715 patients (367 in the AI group, 348 in the control group) from Italy and Taiwan, with a mean age of 59.6 years (51.5% men) showed that WE with AI demonstrated numerical APC enhancement (1.31 ± 1.80 vs. 1.14 ± 1.38 , $P = 0.152$) and significantly increased the detection rate of proximal sessile serrated lesion (SSL) (5.2% vs. 2.3%, $P = 0.044$) in comparison to WE alone (Tables 1 and 2) (Cheng CL et al. Gastrointest Endosc 2024;99:AB17–18).

Table 1. Per-patient ADR and APC in water exchange (WE) with CADe pilot study

Detection of adenomas	WE without CADe (n=348)	WE with CADe (n=367)	P value
Overall ADR, n (%)	203 (58.3)	207 (56.4)	*0.602
Right ADR, n (%)	106 (30.5)	107 (29.2)	*0.703
Proximal ADR, n (%)	132 (37.9)	149 (40.6)	*0.465
Overall APC, mean (SD)	1.14 (1.38)	1.31 (1.80)	[†] 0.152

*Fisher exact test. [†]Student's *t* test

Table 2. Detection of sessile serrated lesions in WE with CADe pilot study

Detection of SSLs	WE without CADe (n=348)	WE with CADe (n=367)	P value
SSL detection rate			
Overall SSL detection rate, n (%)	10/348 (2.9)	21/367 (5.7)	*0.062
Right SSL detection rate, n (%)	7 (2.0)	14 (3.8)	*0.153
Proximal SSL detection rate, n (%)	8 (2.3)	19 (5.2)	*0.044
Detected SSL per colonoscopy			
Right SSL per colonoscopy, mean (SD)	0.02 (0.17)	0.06 (0.36)	[†] 0.062

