During the insertion phase of WE colonoscopy, the air pump will be turned off, while the colon will be irrigated with water using a flushing pump. The WE approach involves the simultaneous infusion of water to facilitate luminal expansion and suction of unclean water during insertion. Any encountered air pockets will be aspirated to ensure optimal WE maneuver in salvage cleaning. Upon reaching the cecum, where most of the water is suctioned to collapse the cecal lumen, the air pump will be opened. All investigators will be asked to adhere to WE technique confirmation of nearly equivalent volumes of water infused and suctioned upon cecal arrival. During the withdrawal phase, air or CO₂ will be insufflated in both arms.

Withdrawal from the cecum will begin in the left lateral position. Similar withdrawal techniques with adequate luminal distention and comprehensive examination will be emphasized. Adhering to prevailing guidelines set by the American and European Societies of Gastrointestinal Endoscopy, a minimum of 6 minutes of clean withdrawal time will be maintained for all colonoscopies across both arms.

During the withdrawal phase, an exhaustive polyp search and subsequent resection will be performed in both study arms. Comprehensive records will be maintained for all detected polyps, capturing size (assessed in comparison with open forceps or snare), precise location, and morphology (classified according to the Paris classification).

False positives of AI: False positive (FP) activation is defined as the identification by AI systems of an area during the withdrawal phase that is not deemed to be a colorectal lesion after re-examination by the colonoscopist. Real-time flagging of FP activation is recorded by investigators and study staff. The NOISE classification will be

used to categorize the causes of FP activations.

Study outcomes: The primary outcome is APC, calculated as the total number of adenomas detected divided by the total number of colonoscopies performed. Secondary outcomes encompass 1) overall ADR, 2) ADR and APC in the right and proximal colon, 3) SSL detection rates, 4) mean number of non-neoplastic lesions resected per colonoscopy, 5) real-time number of FPs per colonoscopy, and 6) procedural times (e.g., insertion time, withdrawal time, and total procedural time).

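### One unrestricted P < 0.05 rule covers some 10 to 12 overlapping secondary comparisons as well as APC, so a nominally significant secondary result is likely enough by chance that the word should be kept for the primary test

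*Combined protocol and SAP*

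**What the plan says.** APC is named as the single primary outcome under Hypotheses and again under Study outcomes, and the Sample size calculation is built on it: "With a two-sided significance level of 5% and 80% power, 376 patients will be required per group (752 randomized patients".

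The Study outcomes section then lists six groups of secondary outcomes. It begins "Secondary outcomes encompass 1) overall ADR, 2) ADR and APC in the right and proximal colon, 3) SSL detection rates" and goes on to resections of non-neoplastic lesions, AI false positives, and procedure times, with insertion, withdrawal and total time given as examples.

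The Statistical analysis section assigns tests by type of variable (t-test or chi-square), adds an adjusted Poisson regression for APC, plans an interim analysis at about 70% of enrollment, and ends with the rule that a P "value < 0.05 is considered significant". Nothing limits that rule to APC. The plan gives no order of testing, no multiplicity adjustment, no statement that secondary outcomes are exploratory or supportive, and no confidence intervals for them.

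**The concern.** Under the rule as written, any secondary comparison that falls below 0.05 may be reported as significant, whatever happens to APC. The comparisons are numerous and overlap, so some will cross the line by chance more often than the nominal 5% suggests. What is at stake is the standing of secondary claims, above all in a report where APC has missed.

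The Introduction shows how such a result can be presented. Tables 1 and 2 hold nine tests. APC gave P = 0.152, and only the two proximal SSL comparisons fell below 0.05 (0.044 and 0.036). The text says that WE with AI "significantly increased the detection rate of proximal sessile serrated lesion (SSL") compared with WE alone. These are background retrospective data and prove nothing about the trial's own analysis, but they illustrate the pattern.

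For non-neoplastic resections and procedure times there is a smaller gap. The plan offers only a difference test, and a difference test alone cannot support a statement that AI causes no increase.

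**Working it through.** **The plan's own figures.** The documents state no familywise error rate, so there is none to reproduce. The dropout inflation reproduces: 752/0.9 = 835.6, rounded up to 836. The 376 per group cannot be checked because no SD or distribution is given. With the stated difference of 0.9 × 0.25 = 0.225, n = 2 × SD² × 7.849/0.225² gives 376 at an assumed SD of 1.10. The multiplicity check does not depend on this; it uses 376 per arm only as the trial size.

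**Counting the secondary comparisons (Study outcomes).**
- ADR: overall, right, proximal = 3
- APC: right, proximal = 2
- SSL detection rates: 3 if overall, right and proximal, as in Table 2; 1 if a single rate is tested
- Non-neoplastic resections = 1
- Times: 3, taking the three examples listed

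The total is 3 + 2 + 3 + 1 + 3 = 12, or 10 with one SSL rate. False positives per colonoscopy are left out: they are defined as AI activations, so the control arm has no counterpart. The first eight in the list are the detection outcomes.

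**Upper reference, if the tests were independent.** The chance of at least one P < 0.05 under no effect is 1 − 0.95^k:
- k = 12: 46.0%
- k = 10: 40.1%
- k = 8: 33.7%

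**Why independence overstates it.** Right-colon findings are part of proximal findings. In the pilot, patients with a right-colon finding as a share of those with a proximal one were 106/132 = 80% and 107/149 = 72% for adenomas, and 7/8 = 88% and 14/19 = 74% for SSL. Total time largely repeats its components.

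**Null simulation with overlap.** 376 per arm, 4,000 simulated trials per scenario, t-tests and chi-square tests as planned. Assumptions not in the documents: gamma-Poisson adenoma counts (gamma shape 1 to 2, mean 0.9 or 1.14), 35/20/45 shares for right, transverse and distal colon, SSL mean 0.04 to 0.10 per patient, gamma-distributed times, total time = insertion + withdrawal, and withdrawal time with or without a link to lesion count.

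| Scenario | Any of 12 | Any of 10 |
|---|---|---|
| Mean 0.9, shape 2 | 32.6% | 30.2% |
| Mean 0.9, shape 1 | 31.9% | 29.6% |
| Mean 1.14, shape 1.5, no time link | 33.2% | 30.7% |
| As first, SSL mean 0.10 | 30.8% | 29.0% |
| As first, continuity-corrected chi-square | 28.6% | 27.3% |

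A separate simulation with other settings (6,000 trials, SSL about 0.05 per patient) gave 34.5% for 12 tests. Together these give the range of 27–35%. A Bonferroni or Holm adjustment over the 12 brings the figure down to about 3–4%.

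**Narrower questions, simulated in the same way.**
- Any of the eight detection outcomes, either direction: about 22%
- Any of the eight favouring AI: about 11–12% (down to 10% in some settings)
- Any of the eight favouring AI, among trials where APC misses: 9–10%

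**The case against.** The strongest reply is that the trial has one named primary outcome, that the hypothesis and sample size rest on it, and that the rest is labelled secondary. Whether secondary outcomes need formal familywise control is partly a matter of convention. This stands to the extent that the primary APC test is not inflated by the secondary comparisons. It does not remove the point, because the rule calls a secondary P below 0.05 significant and no sentence says to read it as merely supportive.

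A reader might infer several stronger things that the documents do not support:

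- **A one-in-three chance of a false AI benefit.** The figure of about one in three counts results in either direction, including fewer adenomas with AI. It also counts insertion time, although AI is switched on only during withdrawal. Dropping insertion time lowers the figure by only 1 to 2 points, but restricting it to a detection benefit cuts it to about 11–12%.
- **A firm count of 12.** Three SSL sites are inferred from the pilot table, and the times are introduced only as examples.
- **That P above 0.05 is taken as proof of no harm.** The plan says only when a result is significant. It neither equates a non-significant result with safety nor labels resections and times as harm outcomes.
- **That the pilot's multiplicity is a fault in this plan.** It is background, and the Introduction calls the pilot APC gain only numerical.

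A further fair objection concerns remedies. Limiting P < 0.05 to APC is not enough in itself: if 0.05 were used at both the 70% look and the end (an assumption, since no boundary is given), the APC type I error would be about 7.6%. The plan also leaves open whether the t-test or the Poisson model decides APC. Both points have to be met in the wording of the fix.

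**Conclusion.** The concern holds for secondary claims. One unrestricted rule covers APC and about 10 to 12 overlapping secondary comparisons. Under no AI effect it would yield at least one nominally significant secondary result in roughly 27–35% of trials. The simulated figures rest on assumed dispersion, segment shares, SSL frequency and time distributions. They were stable across the settings tried, but they are not derived from the documents; the independence figure of 46% should not be quoted as the trial's error rate.

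The primary conclusion is not at risk from this source. This is a worthwhile and inexpensive correction to how results may be described, and it does not point to a flaw in the design.

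**What to change.** Replace the closing sentence of Statistical analysis with wording to this effect:

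> *Statistical significance will be claimed only for the primary comparison of APC, using the single pre-named primary analysis and the significance level remaining after the planned interim analysis. All secondary outcomes are supportive and will be reported as differences or ratios with 95% confidence intervals, without claims of significance. Any statement that non-neoplastic resections or procedure times are not increased will rest on the confidence interval.*

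Two blanks must be filled for this to work: which analysis of APC is primary, and what level the interim analysis leaves for the final test.

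If the sponsor wants to be able to claim a secondary outcome, it should write down a short fixed order of its own choosing before unblinded results are seen. That sequence would be tested only if APC is significant and would stop at the first non-significant result. The order matters. Pilot overall ADR was 56.4% with CADe and 58.3% without, so a sequence starting with ADR could stop before reaching SSL.

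The cost is a change of text, with no change to sample size, data collection or conduct. The downside is that a nominal P < 0.05 on a secondary outcome outside any such sequence can no longer be called significant.
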